Demographically similar pediatric patient groups with varying levels of exposure to the FVPP at baseline will be compared: high exposure (>24 months), moderate exposure (12-24 months), and no previous exposure. Children with no previous exposure will be introduced to the FVPP, and researchers will track changes in dietary intake, food security, and weight status over two years. The specific aims of the study are to (1) compare baseline dietary intake, food security, and weight status between pediatric patients with varying levels of exposure to the FVPP; (2) measure changes in diet, food security, and weight status before and after never-before-exposed children are introduced to the FVPP; and (3) compare mean 12- and 24-month follow-up measures of dietary intake, food security, and weight status in the initial no exposure group to baseline measures in the high exposure group. A central expectation is that greater exposure to this FVPP will promote intake of fruits and vegetables, better food security, and lower rates of childhood obesity.

The current study, in design and approach, is grounded in the theoretical framework of Bandura's Social Cognitive Theory (SCT). SCT explains behavior using a three-stage, dynamic model linking personal factors, environmental factors, and behavior.^{30,31} This study's SCT framework involves collaborations with partnering physicians and local agricultural leaders to support environmental change and social learning. Since children's dietary intake is generally guided by their parents, critically important environmental factors, such as access to fruits and vegetables as well as caregiver modeling of the healthy behaviors, are of particular importance.^{32,33} Consistent with SCT, we also posit that self-efficacy is central to behavior change. Accordingly, self-efficacy for consuming fruits and vegetables, which refers to one's judgment over one's capability to enact the behavior, is important to change dietary behavior.³⁴ By grounding the study with the theoretical framework of SCT, we suggest that pediatrician issuance of a prescription for fruits and vegetables to every child at each office visit will promote food access and self-efficacy to consume healthy foods. Furthermore, pediatrician messaging to children and caregivers will influence health-promoting behaviors linked to increased consumption of fruits and vegetables.

Study Design

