- Clinic 3 is the largest pediatric clinic in Genesee County, with Flint as its urban center. Expansion of the FVPP to clinic 3 will substantially increase program reach among vulnerable children and families living in Flint. Last year, clinic 3 had over 12,000 pediatric visits. It has a comparable patient population to clinics 1 and 2, serving only children in need who are residents of Genesee County.

Participants and recruitment

A sample of 250 caregiver-child dyads presenting at clinic 1, 250 caregiver-child dyads at clinic 2, and 350 caregiver-child dyads at clinic 3 will be assessed for eligibility, with 700 total dyads enrolled (anticipated 10-15% not meeting eligibility and 10% refusal based on a previous study). To control for confounders, we will adopt a balancing strategy that consists of recruiting in the study children who have approximately the same age, sex, and race across the three clinical settings. These children will not be balanced according to variables pertaining directly to the exposures (e.g., duration of FVPP exposure).

With target samples of 200, 200, and 300 caregiver-child dyads enrolled in clinic 1 - high exposure, clinic 2 - moderate exposure, and clinic 3 - no previous exposure, respectively, we have well above 90% power to jointly detect modest relative differences in the baseline mean intake of vegetables of 20% from clinic 2 to clinic 3 and 38% from clinic 1 to clinic 3. This calculation assumes an underdispersed Poisson model with a dispersion parameter of 0.82, derived using previously published data on the mean intake of vegetables of 0.72 cup and a standard deviation of 0.77 cup in the settings with no prior FVPP exposure.²⁰ Likewise, with 300 caregiver-child dyads enrolled in clinic 3, we have well above 90% power to detect a modest temporal improvement in the mean intake of vegetables of 25% over 12 months (0.72 cup at baseline versus 0.90 cup at 12-month follow-up). This calculation assumes a correlated Poisson model for underdispersed count data with timepoint dispersion parameter of 0.82, and a modest temporal correlation of 0.2. Increasing values of the temporal correlation greatly improves the statistical power. Finally, estimation of FVPP effects will specify two-tailed tests with alpha set at the 0.05 level.

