To compare baseline dietary intake, food security, and weight status between pediatric patients with varying levels of exposure to the FVPP, we will collect study measures at baseline from 700 dyads at each of three partnering clinics. To measure changes in diet, food security, and weight status when never-exposed children are introduced to the FVPP, we will follow approximately 200 dyads from clinic 3, collecting study measures at baseline, 12- and 24-month follow-up. In addition to posters, brochures, and websites that explain the FVPP, caregivers at clinic 3 will be reminded of each follow-up visit through reminder cards and telephone calls.

REDCap provides data security measures designed to prevent unauthorized access, disclosure, alteration, and use of data. Data from the completed evaluation tools will be stored in REDCap project database. Children and caregivers will be assigned identification numbers upon enrollment in the study. All data will be de-identified within the data management system, and de-identified data will be exported for analyses.

Any modifications to the approved protocol will be submitted to Michigan State University IRB for review and approval prior to implementation. Furthermore, although the likelihood of any adverse event in this trial is remote, we have formalized our Data and Safety Monitoring Plan to include a designated Data and Safety Monitor. This Monitor will have the authority to recommend termination of the trial if he makes the determination that unacceptable adverse events have taken place. Should any adverse events occur, these will be immediately reported to Michigan State University IRB for review.

Benefits

Completion of our study aims will provide empirical evidence for the effectiveness of Produce Prescription Programs, which were recently added to the US Farm Bill through the Gus Schumacher Nutrition Incentive Program. Our study will share insights regarding the duration and intensity of exposure necessary to influence changes in food security, dietary patterns, and weight status when fruit and vegetable prescriptions are provided to pediatric patients. Furthermore, our results will be especially important to pediatricians and primary care physicians who recognize the consequences of food insecurity among young patients and are seeking tangible solutions that not only provide food to hungry children but ensure that the food provided is high in nutrients needed to support healthy growth and development.

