An alternative balancing strategy based on propensity scores will be used to mitigate potential differences at baseline among participants in the three study groups. These scores will be used to derive an unbiased estimate of the average treatment effect of FVPP on study endpoints. The generalized propensity score to account for multiple levels of treatment in the spirit of Imbens will be estimated with a multinomial logistic regression.⁶² To estimate the FVPP effects, we will use an elaborated multinomial logistic model that includes the child's level, the caregiver's level covariates, and functions thereof (e.g., interactions).

The choice of analytic methods will be guided by the specific aims, the nature of study endpoints and that of relevant data. Independence models will be used to compare baseline dietary intake, food security, and weight status between pediatric patients with varying levels of exposure to the FVPP. Correlated data models will be used to evaluate (1) changes in diet, food security, and

weight status when never-exposed children are introduced to the FVPP; and (2) compare mean follow-up measures of dietary intake, food security, and weight status in the initial no exposure group to baseline measures in the high exposure group.

Comparison of baseline measures based on FVPP exposure

Multiple linear regression will be used to assess the relationship between mean daily intake of fruits and vegetables and level of exposure to the FVPP. A basic logistic regression model will be used to evaluate the adjusted effect of the child-level exposure to the FVPP on the obesity probability. An ordinal logistic regression model will be used to evaluate the adjusted effects of the child-level exposure to the FVPP on food security (measured as an ordinal outcome). Within this class of models, we will entertain the popular proportional odds model with prior evaluation of the assumption of the proportionality of odds across the ordered levels of food security. These analyses will be adjusted for variables such as food assistance program participation, nutrition education program participation, child race, child age, child gender, caregiver-reported income group, caregiver-reported weight status, caregiver education, and child-reported mean daily intake of fruits and vegetables.

Evaluation of changes when children are introduced to the FVPP

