After baseline data collection, periodic follow-up assessments will be conducted to study changes in diet, food security, and weight status among children newly exposed to the FVPP at clinic 3. Because of the repeated nature of the data generated for this aim, we will consider methods that accommodate the within-child and/or the within-caregiver association. For continuous outcomes (e.g., dietary intake), repeated measures models such as linear mixed models and repeated ANOVA models, will be entertained in view of their robustness to certain types of missing data. These classes of models will be used to assess changes from baseline at key points in the study.^{63,64} For ordinal endpoints such as food security (with ordered levels), a generalized linear mixed effects model with cumulative logits will be entertained. To examine whether there is a significant improvement in child-reported food security from baseline, contrast representing the difference in log-odds between baseline and follow-up will be evaluated. Alternatively, GEE counterparts of these likelihood-based models (that use the sandwich-based correction in lieu of the model-based variance-covariance matrix of the parameter estimates) will also be considered.⁶⁵

Comparison of mean follow-up measures in the initial no exposure group to baseline measures in the high exposure group

At follow-up, measures of dietary intake, food security, and weight status in a group of children newly exposed to the FVPP will be compared to baseline measures of children with high exposure to the FVPP (>24 months). For example, to compare measures of dietary intake (at 12 months and 24 months) in the newly exposed group to those of the highly exposed group, the class of linear mixed models and repeated ANOVA models will be considered. These models will be similar to those of aim 2, with the additional flexibility of group-specific time-point effects. For ordinal outcomes (e.g., food security) and binary outcomes (e.g., obesity), a generalized linear mixed effects model will be used. Alternative models such as GEE models will also be entertained.

Discussion

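### Within any one outcome the plan names no deciding contrast or time point: up to seven tests at unadjusted 0.05, and about a 13–20% chance of a false positive over Aims 1 and 2

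*Combined protocol and SAP*

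**What the plan says.** The section on study aims and hypotheses compares three groups, "high exposure (>24 months), moderate exposure (12-24 months), and no previous exposure", and lists three aims without ranking them. Aim 1 compares the groups at baseline. Aim 2 measures change in newly exposed children. Aim 3 is to "compare mean 12- and 24-month follow-up measures of dietary intake, food security, and weight status in the initial no exposure group to baseline measures" of the highly exposed children.

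Under Participants and recruitment, the power statement begins "With target samples of 200, 200, and 300 caregiver-child dyads enrolled" and gives power for detecting two baseline differences jointly (clinic 2 v 3 and clinic 1 v 3), then power for the 12-month change. It closes with "estimation of FVPP effects will specify two-tailed tests with alpha set at the 0.05 level".

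The data collection section has about 200 clinic 3 dyads followed, "collecting study measures at baseline, 12- and 24-month follow-up".

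The Statistical analysis plan says for Aim 1 that "Multiple linear regression will be used to assess the relationship between mean daily intake of fruits and vegetables and level of exposure to the FVPP", and for Aim 2 that "These classes of models will be used to assess changes from baseline at key points in the study". It does not say which contrasts of exposure level are tested, which visit decides, or whether any result is exploratory. Nor does it carry the joint reading of the power statement into the analysis.

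The Benefits section states: "Our study will share insights regarding the duration and intensity of exposure necessary to influence changes in food security, dietary patterns, and weight status". The Discussion repeats this, adds evidence of effectiveness, and expects the results to inform policy on state and federally supported programmes.

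**The concern.** Choosing a single primary outcome would not settle this. For that one outcome there would still be several routes to a positive statement, and they can disagree: an effect at more than 24 months of exposure but not at 12–24, or at the 12-month visit but not at 24. With no deciding contrast, the conclusion can be drawn from whichever comparison crosses 0.05.

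The duration claim is the most exposed. If one visit is significant and the other is not, that pattern is easily read as evidence on how long exposure must last. A difference in significance is not a test of the difference, and the plan contains no direct 24 v 12 month comparison.

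**Working it through.** **Inputs from the documents.** Baseline groups 200, 200 and 300; about 200 followed at clinic 3; visits at 0, 12 and 24 months; two-tailed 0.05; temporal correlation 0.2; mean vegetable intake 0.72 cup, SD 0.77; dispersion 0.82; baseline differences of 20% and 38%; 12-month mean 0.90 cup.

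**Assumptions.** Equal variances under the null, unadjusted normal tests, complete data in the 200 followed, equal correlation between all visits, and a range of 0.2–0.8 for that correlation.

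**1. The plan's own figure.** Dispersion: 0.77²/0.72 = 0.823, as stated. Taking 20% and 38% as increases over 0.72, with variance 0.82 × mean / n:
- Clinic 1 v 3: difference 0.2736, SE = √(0.82×0.9936/200 + 0.82×0.72/300) = 0.0777, z = 3.52, power 94%.
- Clinic 2 v 3: difference 0.144, SE = √(0.82×0.864/200 + 0.82×0.72/300) = 0.0742, z = 1.94, power 49%.
- One joint 2-df test: 90.8%. Both contrasts significant: 48%.

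If the percentages are instead falls to 0.72 (means 0.90 and 1.16), the joint test has 99.9% power and both contrasts 67%. The stated power of over 90% therefore fits one joint 2-df test and does not fit a requirement that both contrasts succeed.

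**2. Counting the tests for one outcome.**
- Aim 1: one joint test, two contrasts with clinic 3, or three pairs. The plan does not say which.
- Aim 2: 12 v 0 and 24 v 0 months.
- Aim 3: clinic 3 at 12 and at 24 months v clinic 1 at baseline.

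This gives five, six or seven tests.

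**3. Dependence.** Seven independent tests would give 1 − 0.95⁷ = 30.2%. These tests share data, so the figure is lower. Correlations between the test statistics include:
- 1 v 3 with 2 v 3: (1/300)/(1/200 + 1/300) = 0.40.
- 12 v 0 with 24 v 0 months: 0.50.
- The two Aim 3 contrasts: (1 + ρ)/2, that is 0.6 at ρ = 0.2 and 0.9 at ρ = 0.8.

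**4. Chance of at least one false positive, no true effect** (simulated z statistics, 200 followed, ρ 0.2–0.8):

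| Family | Either direction |
|---|---|
| Aim 1, three pairs | 12% |
| Aim 1, two contrasts with clinic 3 | 9% |
| Aim 2, two visits | 9% |
| Aim 3, two visits | 7–9% |
| Aims 1–2, joint Aim 1 test + two visits | 13% |
| Aims 1–2, four contrasts | 17% |
| Aims 1–2, five contrasts | 19–20% |
| All aims, joint Aim 1 test (five tests) | 18–19% |
| All aims, seven tests | 23–24% |

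Counting only an apparent benefit, the five tests of Aims 1–2 give about 10%. With 300 followed in place of 200, the seven-test figure at ρ = 0.2 is 23.0%, against 23.8%.

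**5. With a joint test first.** Aim 1 falls to 5.0%, and the two Aim 2 contrasts against baseline to 4.1–4.2%. If clinic 1 truly differs by 38% and clinic 2 equals clinic 3, the false-positive rate for clinic 2 v 3 is 5.0%, so control does not depend on the global null.

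**6. Power cost.**
- Clinic 1 v 3: 94% to 90%. Clinic 2 v 3: 49% either way.
- 12-month change, n = 200: SE = √(0.82 × (0.72 + 0.90 − 2×0.2×√(0.72×0.90))/200) = 0.0730, z = 0.18/0.0730 = 2.47, power 69%. With the gate it is 64% if the 24-month mean stays at 0.90, and 69% if it rises to 0.99. Both 24-month means are assumptions.

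**The case against.** A reader might infer that the plan commits to seven tests and so carries about a 23% chance, nearly one in four, of a false programme effect. The documents do not support that.

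- **Seven is an upper count.** Clinic 1 v 2 appears nowhere as a planned contrast, the power statement treats its two contrasts jointly, and a regression on exposure level can be read with one joint test. Taking the joint Aim 1 test with only the powered 12-month contrast, the chance is about 9.5%.
- **Not every rejection is a programme effect.** By follow-up, both groups in Aim 3 are exposed, so a difference between them is not in itself evidence that the programme works. The 23% also includes results that go against the programme.
- **The aims are separate questions.** Testing each pre-stated question at 0.05 is common practice, so the rates within an aim (7–12%) are the firmer criticism.

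All three stand, and they limit the size of the point. They do not remove it. The plan leaves open whether Aim 1 is one, two or three tests, and does not say which aim or visit supports the effectiveness claim. While either Aim 1 or Aim 2 could support it, the rate over both is relevant.

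A reader might also infer that Aim 2 must be the deciding aim, because only it compares children with themselves. That does not follow. The Study Design section calls this component non-controlled, the Setting section describes pandemic effects on hunger and food insecurity that could change intake over the same period, and its 12-month contrast has less power at n = 200 (69%) than clinic 1 v 3 (94%).

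**Conclusion.** The point holds for the contrasts within a single outcome. Tests of programme effects are set at unadjusted two-tailed 0.05 with no deciding contrast or visit, while the plan promises conclusions on effectiveness and duration. The error rate is roughly twice the nominal level within Aim 2 and within Aim 1 if its contrasts are tested separately, and about 2.6–4 times nominal over the two aims. The highest figure, 23–24%, applies only if all seven tests are run and any rejection in either direction is counted.

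These figures rest on the working assumptions. Covariate adjustment or attrition would move them slightly, and they leave out confounding between clinics. The number of outcomes is a separate matter and would add to them. This should be corrected, but it does not invalidate the design.

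**What to change.** Add to the Aim 1 and Aim 2 subsections of the Statistical analysis plan:

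- **Aim 1.** For each outcome, first test the three-level exposure effect with one 2-df joint test at 0.05. Interpret pairwise clinic contrasts at 0.05 only if it is significant. This matches the joint wording of the power statement. With exactly three groups it is a closed procedure and needs no further adjustment.
- **Aim 2.** First test the 2-df effect of time (0, 12, 24 months) at 0.05, then 12 v 0, 24 v 0 and 24 v 12 months at 0.05. Base any duration statement in this aim on the direct 24 v 12 month contrast, not on which visit is significant.
- **Across aims.** The sponsor states which aim and time point decide effectiveness. The gates hold 5% within each aim for one outcome, not across aims: two gated aims, if independent, would give 1 − 0.95² = 9.75%.
- **Aim 3.** Report it as a benchmark, with estimates and 95% confidence intervals.

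The cost is a few sentences of SAP text, with no new data, visits or participants. The loss of single-contrast power is about 4 points for clinic 1 v 3 and up to about 5 points for the 12-month change if the gain only persists to 24 months.
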